#### 9.5.3. Use of Epinephrine as a Rescue Medication at Exit DBPCFC

The number and percent of pediatric subjects using Epinephrine as a rescue medication at the Exit DBPCFC will be summarized by type of challenge (peanut or placebo) and treatment group. Fisher's exact test will be performed to test for a treatment difference for each type of challenge at the Exit DBPCFC.

This corresponds to the following hypotheses and the analysis at the Exit DBPCFC in pediatric subset of the Completer population will constitute the primary analysis of this secondary endpoint:

- H0: Percentage of active subjects with epinephrine use as a rescue medication at the Exit DBPCFC = percentage of placebo subjects with epinephrine use as a rescue medication at the Exit DBPCFC
- HA: Percentage of active subjects with epinephrine use as a rescue medication at the Exit DBPCFC ≠ percentage of placebo subjects with epinephrine use as a rescue medication at the Exit DBPCFC

The number and percent of pediatric subjects using Epinephrine as a rescue medication at the Exit peanut DBPCFC will be summarized by Epinephrine use at the Screening peanut DBPCFC and treatment group. A logistic regression model will be fit to assess the relationship between epinephrine use at the screening DBPCFC with epinephrine use at the

Exit DBPCFC. Epinephrine use at the Exit DBPCFC will be modelled with terms for treatment, epinephrine use at the Screening DBPCFC, and the interaction between treatment and epinephrine use at the Screening DBPCFC. The odds ratio for epinephrine use at the Exit DBPCFC with 95% CIs of the treatment effect (AR101 versus Placebo) by epinephrine use at Screening will be calculated. Similarly, the odds ratio for epinephrine use at the Exit DBPCFC with 95% CIs of epinephrine use (Yes versus No) at the Screening DBPCFC by treatment will be calculated. The score statistic will be used to calculate a p-value for each of the model terms.

Summary of epinephrine use as a rescue medication at the Exit peanut DBPCFC (yes or no) will also be summarized by each dose level (up through 1000 mg, up through 600 mg, up through 300 mg, etc.). Treatment groups will be compared using a logistic regression model with terms for treatment, epinephrine use at the Screening DBPCFC, and the interaction between treatment and epinephrine use at the Screening DBPCFC, when the dose level under examination has at least 5% of subjects with epinephrine use.

The number of epinephrine doses as a rescue medication during the Exit DBPCFC will be summarized by dose level (up through 1000 mg, up through 600 mg, up through 300 mg, etc.). Doses will be categorized as 0 doses, 1 dose, 2 doses, and 3 or more doses. Treatment groups will be compared using Cochran-Mantel-Haenszel tests (with equally spaced scores).

Listings of all Epinephrine use will be provided, sorted by time Screening DBPCFC and DBPCFC, then by treatment group, and subject ID.

Analyses will be performed in the Completer population.

# 9.5.4. Peanut-specific IgE and IgG4

Blood samples to measure ps-IgE, ps-IgG4 levels, and total IgE levels will be collected prior to the Screening DBPCFC and prior to the Exit DBPCFC. Ps-IgE/IgG4 ratio will be calculated, listed by subject, and summarized by visit and treatment group. Results outside the limits of quantification will be displayed as less than the lower limit of quantification (LLOQ), or greater than the upper limit of quantification (ULOQ), as appropriate. These values will be summarized as either the LLOQ or the ULOQ. If the ps-IgE or ps-IgG4 is outside of the limits of quantification, the ps-IgE/IgG4 ratio will be calculated using the LLOQ or ULOQ as appropriate.

Summary statistics, including geometric means and geometric standard deviations, will be presented by time point and treatment group.

Analyses of change from baseline ps-IgE, ps-IgG4, and ps-IgE/IgG4 ratio will be performed using change calculated on the log10 scale. An ANCOVA model of change from Screening DBPCFC to Exit DBPCFC will be fit with terms for treatment group, region,

and immunoglobulin value at Screening DBPCFC on the log10 scale. Similar analysis methods as described for the change from baseline in MTD at DBPCFC will be used. Geometric least squares mean statistics for the ratio of AR101 to Placebo and geometric least squares mean statistics for the ratio of the Exit DBPCFC to Screening DBPCFC by treatment group will be presented.

The comparison of treatment groups using the ANCOVA model corresponds to the following hypotheses:

- H0: Mean change from baseline within active subjects = mean change from baseline within placebo subjects when controlling for baseline and region
- $H_A$ : Mean change from baseline within active subjects  $\neq$  mean change from baseline within placebo subjects when controlling for baseline and region

Analyses will be performed in the ITT and Completer populations.

## 9.5.5. Peanut Skin Prick Test

Results from the SPT will be listed, including test date, timing of test reading (e.g., 10 minutes), and measurements of the mean wheal diameter (in mm) of the following: peanut wheal (long axis), peanut erythema/flare (short axis), saline wheal (long axis), saline-glycerin erythema/flare (short axis), histamine wheal (long axis), and histamine erythema/flare (short axis).

A derived mean wheal diameter score will be calculated as the average of the long and short axis from the peanut wheal minus the average of the long and short axis from the saline wheal. Summary statistics for the derived SPT mean wheal diameter will be presented at each visit by treatment group for the 15-minute time interval and change from baseline to Exit visit will be presented.

An ANCOVA model of change from baseline at Exit DBPCFC will be fit with terms for treatment group, region, and wheal diameter at baseline. Similar analysis methods as described for the change from baseline in MTD at DBPCFC will be used. Least squares mean change estimates along with 95% confidence intervals will be presented by treatment group and the least squares mean difference (AR101 minus placebo) with corresponding 95% confidence interval will be presented.

The comparison of treatment groups using the ANCOVA model corresponds to the following hypotheses:

• H0: Mean change from baseline within active subjects = mean change from baseline within placebo subjects when controlling for baseline and region

• HA: Mean change from baseline within active subjects ≠ mean change from baseline within placebo subjects when controlling for baseline and region

Analyses will be performed in the ITT and Completer populations.

## 9.5.6. Quality of Life Assessments

Quality of life assessment using the food allergy related quality of life questionnaire (FAQLQ), and the food allergy independent measure (FAIM) questionnaires will be performed at the Baseline and Exit visits.

Separate FAQLQ and FAIM instruments are administered based on the subject's age group. Caregiver/parent versions are also administered for subjects who are 17 years old or younger. Due to differences between the various instruments, separate summaries will be provided by age group and person who completed the questionnaire (i.e., subject or caregiver).

## FAQLQ:

The FAQLQ is a self-report instrument that is intended to assess the effect of food allergy on the subject's quality of life. Evaluations are done by the subject (for subjects 13 years and older) and parent (for subjects 17 years and younger).

The number of items and domains varies by instrument administered. Each question is scored on a seven-point scale (van der Velde et al., 2010). The total score is the arithmetic average of all non-missing items. Domain scores are calculated similarly. The total score ranges from 1 (limited severity perception) to 7 (greatest severity perception). If less than 80% of the items are complete, then the total score will not be calculated. Similarly, if less than 80% of the items within a domain are complete, then the domain score will not be calculated.

Descriptive statistics and scores of total and domain scores along with their changes from baseline will be provided. Data will be summarized separately by age group and responder (subject or caregiver).

Analyses of change from baseline in the total and domain scores will be performed using ANCOVA models of change from baseline at the Exit visit. The model will be fit with terms for treatment group, region, and screening value. Region will be excluded from the model if any region has fewer than 3 subjects with evaluable scores within either treatment group.

Listing of the raw scores as recorded in the CRF will be provided, sorted by treatment group and subject ID.

# FAIM:

The FAIM is a self-report instrument that is intended to reflect the perception of food allergy severity and related risk as evaluated by the subject (for subjects 13 years and older) and parent (for subjects 17 years and younger). The instrument consists of 6 questions (4 expectation of outcome questions and 2 disease severity questions). The parent versions only include the 4 questions related to expectation of outcome. The total FAIM score is calculated as the arithmetic average of all non-missing items and ranges from 1 (limited severity perception) to 7 (greatest severity perception).

Descriptive statistics for each item and the total scores along with their changes from baseline will be tabulated. Data will be summarized separately by age group and responder (subject or caregiver). Analyses of change from baseline in the total score will be performed using ANCOVA models of change from baseline at the Exit visit. The model will be fit with terms for treatment group, region, and screening score. Region will be excluded from the model if any region has fewer than 3 subjects with evaluable scores within either treatment group.

Listing of the raw scores as recorded in the CRF will be provided, sorted by treatment group and subject ID. The comparison of treatment groups using the ANCOVA model for both FAQLQ and FAIM corresponds to the following hypotheses:

- H0: Mean change from baseline within active subjects = mean change from baseline within placebo subjects
- HA: Mean change from baseline within active subjects ≠ mean change from baseline within placebo subjects

Additional exploratory analyses of the FAQLQ and FAIM may be performed. A description of these exploratory analyses will be documented in an addendum SAP for exploratory Quality of Life assessments.

# 9.6. EXPLORATORY ANALYSES

#### 9.6.1. Treatment Satisfaction

Assessment of treatment satisfaction will be performed using the Treatment Satisfaction Questionnaire for Medication (TSQM-9), an exit survey including palatability questions.

The TSQM-9 is a widely used instrument to assess treatment satisfaction with medication in studies where patient reported side effects have a potential to interfere with the objectives of the study. The instrument consists of 9 questions that comprise 3 scales.

Responses to the 9 individual items will be presented using descriptive statistics. The scale scores (effectiveness, convenience, and global satisfaction) will be calculated and summarized using descriptive statistics.

The Effectiveness scale includes items 1-3, the Convenience scale includes items 4-6, and the Global Satisfaction scale includes items 7-9. Each scale will be scored as: 100\*[(sum of non-missing responses) minus the number of non-missing responses] divided by the maximum possible score of the sum of non-missing responses. If more than one item within the scale has a missing result then the scale score will not be calculated.

Analysis of the scale scores will be performed using ANOVA models with terms for treatment group and region.

In addition to the TSQM-9, an exit survey will be performed at study exit. The survey includes questions on study drug palatability, frequency of taking study drug as instructed, impact on attending clinic visits, interest in continuing to take study drug, if the subject would recommend the study drug to others, and burden of treatment. Responses to each item will be summarized with descriptive statistics and type of instrument administered (parent or subject ages 12 and older). No statistical testing is planned for this questionnaire.

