6.5 Exit Visit / Early Discontinuation Visit

Subjects who tolerate 300 mg/d and are maintained at this dose for approximately 24 weeks will return to the clinic for an Exit Visit.

Subjects who fail initial escalation or up-dosing, or who prematurely discontinue treatment, will return to the site for an Early Discontinuation visit that consists of the same procedures as the Exit Visit, but without a DBPCFC. An Early Discontinuation Visit is to occur 14 days from the last dose of study product.

Subjects who withdraw from ARC003 wholly or in part due to intolerable gastrointestinal symptoms, who are not enrolled in the optional saliva study, may be approached at the time of their early termination visit to provide voluntary consent to enroll and participate in the saliva substudy (North America sites only). If this occurs, such subjects will provide a saliva sample as part of the early termination visit and then again during post-OIT follow-up (Table A6 in Appendix 6).

The following procedures will be performed at the Exit/ Early Discontinuation Visit:

• Concomitant medication review

- Diet (food allergen) history
- Completion of the palatability questions
- Completion of the food allergy related quality of life questionnaire (FAQLQ), and the food allergy independent measure (FAIM) questionnaire after the completion of the exit DBPCFC and unblinding for all the patients
- Completion of the Treatment Satisfaction Questionnaire for Medication (TSQM-9) and the exit questionnaire after after the completion of the exit DBPCFC and unblinding for all the active subjects
- Assessment of asthma control in asthmatic subjects using the Asthma Control Test questionnaire
- Physical examination, including weight and height
- Vital signs (blood pressure, pulse rate, body temperature); if DBPCFC is to be conducted, these vital sign measurements should be taken shortly before the first challenge dose
- PEFR (3 attempts are to be performed, and the best value taken). PEFR should, to the extent possible, be measured at the same time as for prior visit assessments.
- Urine pregnancy test, for females of childbearing potential
- Blood draw to collect samples for:
 - Peanut-and peanut-component specific IgE, total IgE, and peanut- and peanutcomponent specific IgG4 measurement (immunoglobulin assays. The amount of blood taken for the immunoglobulin assays will be communicated from the central laboratory and included in the manual of procedures.

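### The TSQM-9 scoring rule in SAP 9.6.1 cannot reach 100, and the planned treatment comparison conflicts with the protocol's collection of the questionnaire from active subjects

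*SAP*

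**What the plan says.** SAP Section 9.6.1 describes the instrument: "The instrument consists of 9 questions that comprise 3 scales". It assigns three items to each scale: "The Effectiveness scale includes items 1-3, the Convenience scale includes items 4-6, and the Global Satisfaction scale includes items 7-9". The scale score is 100 times a bracketed difference, ("sum of non-missing responses) minus the number of non-missing responses"), and that product is "divided by the maximum possible score of the sum of non-missing responses". One missing item per scale is allowed: "If more than one item within the scale has a missing result then the scale score will not be calculated". For analysis the section states: "Analysis of the scale scores will be performed using ANOVA models with terms for treatment group and region".

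The SAP gives no score range, response-option count or item coding for the TSQM-9. The protocol gives no scoring rule.

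On collection, Protocol Section 6.5 has the TSQM-9 and the exit questionnaire completed after "completion of the exit DBPCFC and unblinding for all the active subjects". Footnote r to the Schedule of Events (Protocol Appendix 1) repeats the restriction to active patients. In the same places, the FAQLQ and FAIM (Section 6.5) and the palatability questions (footnote q) are assigned to all patients, so the narrower wording for the TSQM-9 looks deliberate.

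**The concern.** Subtracting the number of answered items makes sense if items start at 1 and the lowest possible score is meant to be 0. Multiplying by 100 makes sense if the highest is meant to be 100. For both to hold, the denominator must be shifted by the same amount as the numerator, and it is not. Every reported scale score would then sit below the value that a 0–100 score would show, and a reader comparing it with 0–100 scores would be misled. Double programming under SAP Section 15 may not catch this, because both programmers would work from the same specification.

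The second problem lies in the same section. A treatment-group term needs scores from both arms, and the protocol directs the questionnaire to one arm.

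**Working it through.** **Inputs.** S = sum of answered items and n = number answered (SAP 9.6.1). M = maximum possible sum of the answered items (SAP 9.6.1). There are three items per scale with at most one missing, so n is 2 or 3. The number of options per item, k, is not in the documents and is varied here as an assumption. Coding 1 to k is also an assumption, suggested by the subtraction of n. There is no stated figure in the plan to reproduce.

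**Formula as written.** Score = 100(S − n)/M. At the top response S = M, so the ceiling is 100(M − n)/M = 100(1 − n/M). Since n > 0, this is always below 100. If all items have k options, M = nk and the ceiling is 100(k − 1)/k.

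**Formula with the shift in both places.** Score = 100(S − n)/(M − n). With coding 1 to k this is 0 at S = n and 100 at S = M.

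| k (assumed) | Ceiling as written | Shortfall from 100 | Ceiling with M − n |
|---|---|---|---|
| 4 | 100 × 9/12 = 75.0 | 25.0 | 100 |
| 5 | 100 × 12/15 = 80.0 | 20.0 | 100 |
| 6 | 100 × 15/18 = 83.3 | 16.7 | 100 |
| 7 | 100 × 18/21 = 85.7 | 14.3 | 100 |
| 10 | 100 × 27/30 = 90.0 | 10.0 | 100 |

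**Other coding.** If items were coded from 0 to k − 1, then M = 3(k − 1). For k = 5 the range would be 100(0 − 3)/12 = −25.0 to 100(12 − 3)/12 = 75.0. For k = 7 it would be −16.7 to 83.3. The ceiling is still below 100, and the floor becomes negative.

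**Effect on results.** The score as written equals the 0–100 score times (M − n)/M. With complete responses that factor is the same for every subject on a scale, so means, differences and SDs all shrink by it and ANOVA p-values are unchanged. For k = 4 to 10 with equal option counts the factor is 0.75 to 0.90.

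**Missing items.** If all items on a scale have the same k, n/M = 1/k whichever item is missing, and the ceiling does not move. It moves only if option counts differ. For an assumed scale with 5, 5 and 7 options:

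- complete: 100 × (17 − 3)/17 = 82.4
- 7-option item missing: 100 × (10 − 2)/10 = 80.0
- one 5-option item missing: 100 × (12 − 2)/12 = 83.3

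**Who has a score.** This part is a comparison of texts.

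- Protocol 6.5 and Appendix 1 footnote r: active subjects, after the exit challenge and unblinding.
- Protocol 6.5 also gives the Early Discontinuation Visit the Exit Visit procedures without the food challenge, and Appendix 1 lists the TSQM-9 under a combined Exit/Early Discontinuation column.
- SAP 2.5 keeps subjects who stop before the exit challenge blinded until database lock, so a site could not limit that visit's questionnaire to active subjects.

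Placebo scores could therefore come only from early discontinuations, if at all. They would be given blind by subjects who stopped, and set against scores that are mostly from AR101 completers who knew their treatment. That is not a randomized comparison.

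**The case against.** The strongest reply is that the documents set no standard that the formula breaks. The SAP states a 1-to-7 range for the FAQLQ and FAIM and an explicit 0–100 transformation for the PEESS, but no range for the TSQM-9. This stands in part: a 0–100 target is inferred from the factor of 100 and the subtraction of n. The inference is strong, because neither step serves a clear purpose otherwise.

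A programmer might also take the maximum possible score to mean the maximum of the bracketed difference, which would give 0–100. The wording names the sum, so the literal reading is the unshifted one. The alternative reading is still a reason to correct the text, and it means that wrong programmed scores are likely but not certain.

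The impact is small. The endpoint is exploratory and outside the testing hierarchy, the nine items are also summarized individually, and constant scaling leaves within-scale tests untouched. All of this stands.

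Two stronger readings are tempting. A reader might infer that the three scales are not comparable with one another. That follows only if their option counts differ, and the documents do not say. A reader might also infer that the treatment term cannot be estimated at all. The early-discontinuation provisions leave room for a few placebo responses, so the documents support a conflict and the lack of a valid comparison, but not strict impossibility.

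**Conclusion.** Wrong as written, low severity. The literal scoring rule caps every TSQM-9 scale at 100(1 − n/M); that conclusion needs no assumption about coding or option counts. The size does: with items coded 1 to k and k between 4 and 10, a top-rating subject scores 10 to 25 points below the implied 0–100 range, and descriptive means, differences and SDs shrink in proportion. Within-scale p-values are unaffected for complete responses. Differences in ceiling between scales, or between subjects with a missing item, arise only if option counts differ.

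The treatment-group term in the ANOVA conflicts with Protocol 6.5 and Appendix 1 footnote r. Few or no placebo scores would exist, and any that did would not support a randomized contrast. This matters more than the small inferential effect of the scaling suggests, because the AR101 descriptive scores then become the main output, and those are what the scaling distorts.

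**What to change.** In SAP 9.6.1, change the denominator to the maximum possible sum of the non-missing responses minus the number of non-missing responses. State that scores run from 0 to 100, and state the item coding and option counts on which this rests.

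Replace the ANOVA with an AR101-only descriptive summary, by region if wanted. If a treatment comparison is intended, reconcile the SAP with Protocol 6.5 and Appendix 1 footnote r, and say whether subjects attending an Early Discontinuation Visit complete the TSQM-9.

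The scoring correction and the AR101-only summary cost a line or two of SAP text and code, with no change to data collection.

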## 9.6.2. Secondary Efficacy Endpoints Analyzed in Adults and Overall

Analyses described above for key secondary efficacy and other secondary efficacy endpoints will be repeated in adults (Ages 18-55) as exploratory analyses. Selected analyses may be repeated overall (pediatric and adult subjects, Ages 4-55). Where appropriate, age group (pediatric or adult) will be included as a factor in the relevant statistical models and as a stratification factor in the statistical tests. Treatment by age group interaction terms will also be included in the models. This will only be applicable for the analyses based on all subjects, if performed.

#### 9.6.3. Baseline Factors that may Influence Desensitization

The influence of age, region and other potentially prognostic baseline factors on treatment group differences in the desensitization response rate and MTD at Exit DBPCFC may be explored using the methods described in sections 9.6.4 and 9.6.5. If done, the analyses will be performed in the pediatric subject subset.

The factors to be explored will be:

- Pediatric age group (age <12,12-17)
- Age as a continuous variable
- Region
- Sex
- Sex by Age group
- MTD of peanut protein at Screening DBPCFC, in log10 scale

- Presence of asthma, as recorded as part of non-peanut allergy history
- Presence of allergic rhinitis, as recorded as part of non-peanut allergy history
- History of allergy to a food other than peanut, as recorded as part of the non-peanut allergy history
- Severity of the peanut allergy, defined as the number of anaphylactic reactions to peanut experienced, divided by the duration of the peanut allergy, and categorized into: subjects with 0 anaphylactic reactions, those with at least one reaction but less than 1 every 5 years, and those with more than 1 reaction every 5 years
- Duration of peanut allergy in months, as recorded as part of allergy history
- ps-IgE level at baseline, in log10 scale
- ps-IgE group (based on a cutoff predictive of screening MTD ≤30 mg as determined from the Screened Population, see Section 9.6.7)
- Mean SPT peanut wheal diameter at baseline
- BMI at baseline
- Use of epinephrine at the Screening DBPCFC
- GI symptoms as part of the Screening DBPCFC reaction
- Presence of eczema / atopic dermatitis, as recorded as part of non-peanut allergy history

The examination of age group and region are considered supportive and not exploratory.

If necessary, categorical variables will be pooled such that each pooled level will have at least 3 observations for each treatment group.

For nominal categorical variables, pooling will start with the smallest level which will be pooled with the next larger level until each pooled level has at least 3 observations for each treatment group. For ordinal categorical variables, pooling will proceed in the same manner but will start with the minimum ordinal value and pool in ascending order. Ties will be broken by sorting (in ascending order) the desensitization rate for AR101, then by the desensitization rate for placebo, then by the geometric mean of the MTD for AR101, and then by the geometric mean of the MTD for placebo. If the tie is still not broken, then tied levels (that are subject to pooling) are pooled together as the initial step.

If model parameters for a categorical variable are not estimable, then the minimum number of observations requiring at least 3 observations per pooled level for each treatment group will be increased by 1 in the above pooling algorithm until the model parameters are estimable. If the model parameters for a binary categorical variable are not estimable, then that factor will not be explored for its effect.

